4.2.1 Primary Outcome Variables/Endpoints

The following are the primary outcome variables and associated measures that will be administered at all three time points (i.e., baseline, 3-months post-baseline, and 6-months post-baseline) in the study:

- LGBTQ Clinical Skills Competency
 - Sexual Orientation Counselor Competency Scale (SOCCS) – Clinical Skills subscale – 11-items from a psychometrically validated measure, based on a 7-point Likert scale assessing the extent to which respondents endorse clinical competence as related to their skills in working with clients of diverse sexual identities. For the present study, items have been adapted to specifically assess competence in clinical skills based on an LGBTQ-affirmative CBT framework.
 - Deliberate Practice of LGBTQ-Affirmative CBT Skills: 2 brief video clips (less than 1 minute each) of fictional clients will be presented. Participants will be asked to write a brief paragraph describing what clinical approaches they would use in their clinical treatment in order to address the challenges

discussed by the fictional client. These written responses will be used to assess participants' LGBTQ-affirmative CBT skills.

- Cultural Humility
 - Multidimensional Cultural Humility Scale (MCHS) – a 15-item self-report psychometrically validated measure assessing the extent to which respondents endorse an ability to maintain an other-oriented, interpersonal stance in relation to cultural identities most salient to clients. For the present study, items were adapted to specifically assess cultural humility as related to working with LGBTQ clients.
- Content Knowledge, Familiarity, and Use of Minority Stress & CBT
 - Minority Stress Content Knowledge Quiz – 10 multiple choice items developed by the researchers for the purpose of this study to assess respondents' content knowledge of minority stress
 - CBT/LGBTQ-Affirmative CBT Content Knowledge Quiz – 10 multiple choice items developed by the researchers for the purpose of this study to assess respondents' content knowledge of CBT/LGBTQ-affirmative CBT
 - Familiarity and Use of LGBTQ-Affirmative CBT Skills Questionnaire – 14 items rated on a 5-point Likert scale that was developed by the researchers for the purposes of this study assessing respondents' familiarity with and use of LGBTQ-affirmative CBT skills

4.2.2 Secondary and Exploratory Outcome Variables/Endpoints (if applicable)

The following are the secondary outcome variables and associated measures that will be administered in the study:

- Acceptability of LGBTQ-affirmative CBT Training
 - Acceptability of LGBTQ-affirmative CBT Training Questionnaire (*only* administered immediately after the training) – Participants will be asked to report how many of the 11 training sessions they attended. Participants will then be asked 2 qualitative questions in regard to which of the 11 training sessions they found most and least helpful. Participants will also be asked 7 questions based on a 5-point Likert scale regarding their interest and perceived benefit from the training. All items were self-developed by the researchers for the purpose of this study.
 - Training in LGBTQ-Affirmative CBT – Session Feedback Forms (administered immediately after each training session) – Participants will be asked at the end of each training session to complete an online feedback form about the session, including providing feedback in regard to participants' satisfaction with the instruction, team members leading the training, and learning activities. This feedback form was developed by the researchers for the purpose of this study.

5 Study Participants

5.1 Study Population

The study population will consist of healthy participants who are 18 year of age or older, fluent in English, and currently in the role of an MHP at an LGBTQ community center in the

U.S. engaging in treatment with LGBTQ clients. MHPs from LGBTQ community centers will specifically be recruited for this study in order to provide evidence-based LGBTQ-affirmative training to MHPs working predominantly with individuals from the LGBTQ community.

5.2 Number of Participants

We plan to enroll at least 76 participants ($n = 38$ per training group). Our team's prior pilot studies assessing the efficacy of LGBTQ-affirmative health trainings demonstrated moderate-to-large effect sizes in improving healthcare providers' LGBTQ-affirmative clinical skills and willingness to provide LGBTQ-affirmative clinical care ($d = 0.66-1.20$; Lelutiu-Weinberger, [name], & [name], in preparation; Lelutiu-Weinberger & [name], 2017; White Hughto, [name], et al., 2017). Based on the most conservative effect size drawn from our team's previous LGBTQ-affirmative training studies for healthcare providers ($d = 0.66$), we conducted a power analysis for an independent samples t -test used to compare the mean of a continuous measurement in two samples. We set the threshold probability for rejecting the null hypothesis (type I error rate) to α (two-tailed) = 0.05. Power to detect Type I error was fixed at a standard level of $1 - \beta = 0.80$ (type II error rate). Given these parameters, we require 38 participants per group ($N = 76$) to retain statistical power. We expect to enroll at minimum 38 participants per group; due to the high need and reach of our recruitment partner (i.e., CenterLink, the coordinating hub of 250+ LGBTQ community centers in the U.S.), we expect to enroll at least 100 participants which will allow for adequate statistical power even with 20% attrition.

5.3 Eligibility Criteria

In order to be eligible for inclusion in the study, an individual must meet all of the following criteria:

- 18+ years old
- Fluent in English
- Mental health provider (including, but not limited to licensed practicing counselors, licensed clinical social workers, licensed marital and family therapists, clinical/counseling psychologists, pre-doctoral psychology interns, third-year or greater graduate practicum students/externs)
- Currently practicing within, or in collaboration with, an LGBTQ community center that is coordinated by CenterLink, the coordinating hub for LGBTQ community centers in the U.S.

Any individual who meets any of the following criteria will be excluded from participation in this study:

- Individuals unwilling or unable to give informed consent at the time of participation and/or not fitting the eligibility criteria outlined above

5.4 Recruitment Procedures

Recruitment of MHPs will be coordinated in collaboration with [name], Director of LGBTQ YouthLink at CenterLink, which is the coordinating hub for over 250 LGBTQ community centers in the U.S. Specifically, a recruitment e-flyer (see attached e-flyer) will be sent by [name] to executive directors at CenterLink community centers throughout the U.S., who will then be asked to send the e-flyer to eligible staff members within their centers. The recruitment e-flyer includes dates/times of the trainings, information regarding the research design (i.e., immediate training group and waitlist control group), as well as information about receiving continuing education credits for participating in the training. Interested participants will be directed to click on a QR code on the recruitment flyer that will direct them to complete an initial online screener (see attached initial online screener) that will ask for their name, email address, age, degree, provider title, and name of their CenterLink community center.

5.5 Consent/Assent Procedures/HIPAA Authorization

Consent will be obtained online via the secure Yale Qualtrics survey software. As such, a waiver of documentation of consent is planned for this study. As previously described, participants will first complete an initial online screener (see attachments on IRES for initial online screener) to express their interest in the training and/or an informational webinar via Zoom on October 2 at 9am PST / 12pm EST to learn more about the training. No research data will be collected at the informational webinar. The initial online screener will also be used to determine eligibility for the training and associated research study. Upon receiving email addresses from interested participants, the research team will contact eligible participants with an anonymized link directing them to the study consent form two weeks prior to the first training session. Any ineligible participants will be contacted and informed of the reason for their ineligibility in this study.

At this point, participants will review the online consent form and have the option to participate or decline participation in the study (see attachments on IRES for online consent form). MHPs will still have the option to receive the training whether or not they consent to and complete the assessment measures. For MHPs who want to attend the training, but do not want to participate in the study, the online consent form will end and no data will be collected from these providers due to them not consenting to participate in the study.

Participants will be informed on the consent forms that they will receive \$50 for completing the baseline measures, \$50 for completing the 3-month post-baseline measures, and \$50 for completing the 6-months post-baseline measures (total = \$150). All study payments will be in the form of e-mailed Amazon gift cards or Venmo payments. Venmo payments will be sent to participants from the private @Yale-Study account and will be accompanied with the text "Thank you for your participation."

Participants will be provided with the PI's contact information and directed to call or email the PI if they have any questions or concerns. The PI will be responsible for ensuring that online consent has been obtained.

Potential participants will be required to check one of the following boxes before moving on to the baseline assessment measures part of the research study:

- YES. I have read the above information. The study has been explained to me. My questions have been answered. I VOLUNTARILY AGREE to be in this study.
- YES. I agree to participate in the online training, but I do NOT agree to take part in the measures associated with the research study.
- NO. I do NOT agree to participate in the online training and associated research study.

6 Study Methods/Procedures

6.1 Study Procedures

A 3-time point longitudinal design will be used for both the immediate training group and waitlist control group with assessment measures administered at each time point (T1: baseline; T2: 3-months post-baseline; T3: 6-months post-baseline). As previously discussed, interested participants will complete an initial online screener. Data collected on this brief online screener will be used to determine eligibility based on the previously listed inclusion criteria, as well as to collect email addresses to contact participants about the training. Data from the initial online screener will not be merged or included with subsequent data collected during the study.

Participants will be contacted via email approximately two weeks prior to the start of the training and informed via the online consent about the research study, including risks and benefits of the study. Participants will still have the option to participate in the training and receive continuing education credits whether or not they consent to and complete the research study measures. The 11 training sessions in terms of content will be no different for those who consent to participate in the study compared to those who choose not to participate in the study. For those who do not provide consent to the study, no data will be collected from these individuals at the three time-point surveys. For those who do provide consent, participants will complete the baseline surveys (T1) via a web-based survey link to the secure Yale Qualtrics survey software. Participants will be told that they do not have to answer any question they do not wish to. Participants will be assigned a unique code number. The use of the unique code will permit linkage of the data being collected across three time points in the study. A master link file will connect participant email addresses to their study code number. The link file will be password protected and only accessible to the PI. All materials will be stored on a password-protected digital folder. Data will be organized in Microsoft Excel, SPSS files, or SAS files and stored on a password-protected computer.

The PI and three postdoctoral psychologists will lead the 11-week LGBTQ-affirmative CBT training (scheduled for October 30, 2020 – January 29, 2021, excluding holidays of November 27, December 25, and January 1) for participants randomized to the immediate training group (see Table 1 in Section 11.1 with more information regarding the content of each of the training sessions). At 3-months post-baseline (i.e., following the immediate training group's completion of the training), the 3-months post-baseline measures will be sent to participants in both the immediate training group and waitlist control group. Participants randomized to the waitlist control group will subsequently receive the second iteration of the 11-week LGBTQ-affirmative CBT training (scheduled for March 5, 2021 – May 21, 2021, excluding the holiday of April 9). At 6-months post-baseline (i.e., following the waitlist control group's completion of the training), the 6-months post-baseline measures will be sent to participants in both the immediate training group and waitlist control group.

See Table 2 in Section 11.2 for a Visit Schedule Table with study procedures listing the points of data collection.

6.1.1 Data Collection

All data collection will occur online via the secure Yale Qualtrics survey software. Data collection will begin with the initial online screener that potential participants will be able to access via a QR code on recruitment e-flyer that will be sent by directors of LGBTQ community centers.

Baseline assessment measures will be sent via email one month prior to the first iteration of the training. The 3-months post-baseline measures will be sent after January 29, 2021 (i.e., after the last session of the training for the immediate training group). The 6-months post-baseline measures will be sent after May 21, 2021 (i.e., after the last session of the training for the waitlist control group). Participants will have a two-week window to complete the study measures at each time point. None of the study measures require licensure for their administration. All measures can be found in the "Measures Packet" uploaded with the study protocol.

At baseline, all participants will be given a unique code that will serve as their study ID for the duration of the study. The use of the unique code will permit linkage of the data being collected across the three time points in the study. A master link file will connect participant email addresses to their study code number. The link file will be password protected and

only accessible to the PI. All materials will be stored on password protected folders on Yale Secure Box that requires dual-factor authentication to access.

6.2 Method of Assignment/Randomization (if applicable)

Participants who are confirmed to be eligible via the online screener and provide informed consent to take part in the study will then be randomized via the randomizer feature of Qualtrics, which will be programmed to evenly assign participants to the immediate training group or the waitlist control group. Our team has successfully used the Qualtrics randomizer for previous waitlist-randomized-controlled trial (e.g., see [name] et al., 2020).

6.3 Adverse Events Definition and Reporting

Adverse event means any untoward medical occurrence associated with the use of an intervention in humans, whether or not considered intervention-related. An adverse event (AE) or suspected adverse reaction is considered "serious" if, in the view of either the investigator or sponsor, it results in any of the following outcomes: death, a life-threatening adverse event, inpatient hospitalization or prolongation of existing hospitalization, a persistent or significant incapacity or substantial disruption of the ability to conduct normal life functions.

This proposed study presents minimal risks to the participants, and as such, adverse events are not anticipated. In the unlikely event that such events occur, the PI will apprise fellow investigators and study personnel of all adverse events, such as loss of confidentiality, that occur during the conduct of this research project via email as they are reviewed.

6.4 Reaction Management

Participants experiencing mild distress during the assessments or training can take a break or complete the assessment at a later date. In the unlikely event that a participant experiences considerable distress, we will make a referral (if needed) for clinical assessment and/or counseling. Participants will be given the names and office phone numbers of the PI and the IRB managers of research and compliance. Of note, given that all participants will be MHPs connected with LGBTQ community centers, it is probable that they will already be knowledgeable about mental health services in their area. In the event that a participant discloses abuse or intent to harm oneself or others, the PI will report disclosures of abuse or intent to harm to the appropriate authorities immediately. Identified clinically trained staff members, including [name], a licensed clinical psychologist, will be on call for emergency consultation. In the unlikely event that such an incident should occur, we will notify the Yale IRB within 5 days and appropriate measures will be taken, including necessary reporting to the IRB.

6.5 Withdrawal Procedures

Of the participants who are eligible and consent to the research study, participants will be able to withdraw from the study at any point. The online consent form will clearly state the voluntary nature of the study and possibility of withdrawal at any point. Additionally, participants will have the option of having their data destroyed.

6.6 Locations/Facilities

The training and online surveys will be completed from the participants' electronic devices (e.g., phones, tablets, or computers). All trainings will be conducted via the PI or postdoctoral researchers' Yale-affiliated Zoom videoconferencing accounts and require a passcode to enter. All measures will be conducted utilizing the secure Yale Qualtrics online survey software.

7 Statistical Design

7.1 Sample Size Considerations

Our team's prior pilot studies assessing the efficacy of LGBTQ-affirmative health trainings have demonstrated moderate-to-large effect sizes in improving healthcare providers' LGBTQ-affirmative clinical skills and willingness to provide LGBTQ-affirmative clinical care ($d = 0.66-1.20$) (Lelutiu-Weinberger & [name], 2017, Lelutiu-Weinberger, [name] & [name], in preparation; White Hughto, [name], et al., 2017). Based on the most conservative effect size drawn from our team's previous LGBTQ-affirmative training studies for healthcare providers ($d = 0.66$), we conducted a power analysis for an independent samples t -test used to compare the mean of a continuous measurement in two samples. We set the threshold probability for rejecting the null hypothesis (type I error rate) to α (two-tailed) = 0.05. Power to detect Type I error was fixed at a standard level of $1 - \beta = 0.80$ (type II error rate). Given these parameters, we require 38 participants per group ($N = 76$) to retain statistical power. We expect to enroll at minimum 38 participants per group; due the high need and reach of our recruitment partner (i.e., CenterLink, the coordinating hub of the United States 250+ LGBTQ community centers), we expect to enroll at least 100 participants which will allow for adequate statistical power even with 20% attrition.

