7.2 Planned Analyses

We will assess training efficacy using an intent-to-treat analysis including all eligible cases. First, to determine randomization effectiveness, differences in baseline demographic characteristics will be assessed between the immediate training and waitlist control conditions using t -tests for continuous measures and chi-square tests for categorical measures. Any differences in baseline demographic characteristics between the groups will be retained as covariates in subsequent analyses. Dependent variables, all of which are assessed as continuous outcomes documenting domains of Clinical Knowledge and Skills of LGBTQ-affirmative CBT, will be assessed for normality using skewness and kurtosis thresholds of ± 2 . If any continuous outcomes are found to be non-normally distributed, we will transform these variables for further statistical tests and reassess skewness and kurtosis after transformation.

In a first set of analyses, we will use linear mixed models with maximum likelihood estimation and we expect to utilize a compound symmetry covariance structure (although final covariance structure will selected based on fit criteria, i.e., lowest Akaike information criterion [AIC]) to test the Condition \times Time interaction for all training outcomes). To do so, we will limit the data to baseline (time = 0) and 3 months post-baseline assessment (time = 1) and examined the Condition \times Time interaction effect of receiving immediate training (condition = 1) versus receiving the 3-month waitlist (condition = 0). Thus, the estimate of interest compared pre-training to immediate post-training outcomes in the immediate training group to pre-waitlist and immediate post-waitlist outcomes in the waitlist control group. Effect sizes (d) for linear mixed models will be calculated as mean pre–post change in the immediate training group minus the mean pre-post change in the waitlist control group, divided by the pooled baseline standard deviation.

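### The stated 80% power is for a two-sample t-test of means; it carries over to the planned Condition × Time test only if the pre-post correlation is about 0.5 or more, and the enrolment minimum of 76 leaves no margin for attrition.

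*Protocol*

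**What the plan says.** On sample size, Protocol 7.1, repeated in the Synopsis and in 5.2, states "we conducted a power analysis for an independent samples" t-test, "used to compare the mean of a continuous measurement in two samples". The inputs are d = 0.66 (the smallest effect from the team's earlier training studies), two-sided alpha 0.05 and power 0.80. The result is 38 per group, 76 in total.

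Section 5.2 then uses that same total as the enrolment minimum: "We plan to enroll at least 76 participants". All three places add that at least 100 are expected, "which will allow for adequate statistical power even with 20% attrition".

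Protocol 7.2 specifies a different efficacy test: the Condition × Time interaction in a linear mixed model limited to baseline and the first follow-up. The effect size is the difference between arms in mean pre-post change, "divided by the pooled baseline standard deviation". The SAP (Intervention Efficacy) keeps this test and this standardiser, with the first follow-up moved to 4 months. Protocol 7.7 drops cases with missing outcomes. Neither document gives a pre-post correlation for any outcome, and 7.1 does not say which SD standardises the 0.66.

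**The concern.** A two-sample t-test on one measurement and a test of the difference in change have different standard errors. The first depends on the outcome SD alone. The second also depends on how strongly baseline and follow-up scores are correlated. A power figure computed for the first does not describe the second until that correlation is stated.

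The enrolment minimum is a separate matter. If 76 people must be analysed and 76 is also the fewest to be enrolled, any loss takes the analysis below the required number.

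What is at stake is how null results are read. The primary outcomes include two 10-item quizzes and a questionnaire built for this study, as well as coded written responses to video clips. A reader told that the design has 80% power will apply that figure to each of them, although the documents do not establish it for the test actually planned.

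**Working it through.** **Inputs.** From Protocol 7.1: d = 0.66, two-sided alpha 0.05, power 0.80, 38 per group, 20% attrition, 100 expected. From 5.2: minimum 76. From 6.2: even allocation. From 7.2: interaction test, d on the pooled baseline SD. The correlation r is not in the documents, so it is varied from 0.3 to 0.7 as an assumption.

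**Step 1: the protocol's own figure.** By the normal approximation, n = 2(1.960 + 0.842)²/0.66² = 36.04, so 37 per group. The exact noncentral t gives 79.98% at 37 and 81.0% at 38. The stated 38 reproduces.

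**Step 2: the planned test.** With complete pairs and equal variances σ² at both times, the interaction estimate is the difference in mean change. The SD of change is σ√(2(1−r)), so the standardised signal is 0.66/√(2(1−r)):

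- r = 0.3: 0.66/1.183 = 0.558
- r = 0.4: 0.66/1.095 = 0.603
- r = 0.5: 0.66/1.000 = 0.660
- r = 0.6: 0.66/0.894 = 0.738
- r = 0.7: 0.66/0.775 = 0.852

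At r = 0.5 the two tests coincide. Noncentral-t power with these signals:

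| Analysed per arm | t-test of means | r = 0.3 | 0.4 | 0.5 | 0.6 | 0.7 | r needed for 80% |
|---|---|---|---|---|---|---|---|
| 38 | 81% | 67% | 74% | 81% | 89% | 96% | 0.49 |
| 40 (100 enrolled, 20% lost) | 83% | 69% | 76% | 83% | 90% | 96% | 0.46 |
| 30.4 (76 enrolled, 20% lost) | 72% | 57% | 64% | 72% | 81% | 90% | 0.59 |

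Rounding the last row down to 30 per arm gives 71% for the t-test and r = 0.60 for 80%. Simulation of the change-score test (20,000 runs per cell, at 30, 38 and 40 per arm) agrees with the formula to within about half a percentage point.

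**Step 3: attrition.** 100 × 0.8 = 80, which exceeds 76. 76 × 0.8 = 60.8, about 30 per arm. 76/0.8 = 95, or 96 for equal arms. At the minimum, one loss per arm leaves 37, where the t-test has 79.98%.

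**Step 4: retained baseline rows.** If the mixed model keeps the baseline scores of participants who drop out, rather than dropping those cases as 7.7 says, the r needed for 80% is about 0.56 with 38 at baseline and 30 at follow-up per arm, and about 0.41 with 50 and 40 (normal approximation).

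**Step 5: the sample in the SAP.** The SAP reports 121 participants (61 and 60). It gives no count of completers at 4 months for the efficacy outcomes, so two rough proxies are used, both assumptions. The 52 and 44 acceptability respondents give 77% power at r = 0.3 and 89% at r = 0.5, with 80% reached at r of about 0.35. The 189 simulated-practice responses at 4 months, at two clips each, suggest about 94 people; at 47 per arm, 80% is reached at r of about 0.36.

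**The case against.** The strongest reply is that nothing in the protocol is miscalculated. The 38 per group is right for the test named. Attrition is addressed in the same sentence, because the claim of adequate power is tied to 100 enrolled, and 80 remaining exceeds 76. For r above about 0.5 the t-test calculation is conservative for the interaction. The documents give no test-retest figure that would place r below that value for the quizzes or the coded responses. All of this stands.

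The r condition also rests on reading 0.66 as standardised by the baseline SD. Section 7.2 defines this trial's d that way, but 7.1 does not say how the earlier studies' d was formed. If it was standardised by the SD of change, the t-test calculation applies directly and no r condition arises. This also stands, and it is a reason to state the scale.

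Three stronger conclusions are tempting and are not supported:

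- A reader might infer that the trial cannot have 80% power at 76 enrolled. It can: 76 complete cases give 81% at r = 0.5, and 76 less 20% reaches 80% at r of about 0.6.
- A reader might infer that the protocol ignored dropout. The gap is at the minimum only, not at the expected enrolment.
- A reader might infer that the trial as run was underpowered. With 121 participants the minimum did not bind, and on the proxies above 80% needs r of only about 0.35.

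What survives is narrower. The published power figure belongs to a test that is not the planned efficacy test, the assumption linking the two is unstated, and one number is used for two different purposes.

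**Conclusion.** The point holds as a gap in the stated justification. It is not an arithmetic error and not a fault in the choice of estimator.

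The stated 80% transfers to the Condition × Time test only if r is about 0.49 or more at 38 per arm analysed, or 0.46 or more at 40. Below that it is too favourable, with 67% and 69% at r = 0.3; above about 0.5 it is conservative. This part assumes that 0.66 is on the pooled baseline SD, that variances are equal at both times, and that cases are complete.

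The point about the minimum needs no assumption about r. At 76 enrolled with the protocol's own 20% attrition, its own t-test has about 71–72% power.

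The practical weight is reduced because 121 participants entered the analysis. The text should still be corrected, since it tells readers how much weight a null result can bear.

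**What to change.** In the Synopsis, 5.2 and 7.1:

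- Restate power for the Condition × Time test. Name the SD that standardises 0.66 and the pre-post correlation assumed, with its source, and show power over r = 0.3 to 0.7.
- Relabel 76 as the number to be analysed, corresponding to 95 enrolled (96 for equal arms) at 20% attrition.

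Do not substitute a single figure of 72% for the minimum. That value holds only for the t-test, or for the interaction at r = 0.5, and would again leave the correlation unstated.

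The cost is about two sentences, carried through three places. The relabelling calls for no extra enrolment, since the protocol already expected 100 and the SAP reports 121, and the estimator does not change. The only price is that the stated power becomes less favourable if the correlation named is below about 0.5.
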